Study Intervention:	
 
• Photosensitizer application, followed by fluorescence photography and photodynamic therapy (PHT) (1x) over 15 minutes at the dermatology ward
 
• Skin swabs
 
• Skin biopsies in only 5 participants
 

Reference Intervention:	From a current prospective study at the University Hospital Balgrist, we have the reference database of colonizing bacteria in the groin without photodynamic treatment. In addition, we will take skin swabs before and after skin antisepsis without antisepsis in 10 participants.
Number of Participants with Rationale:	Aim: 20 volunteers There will be only descriptive statistics to see if numbers of colonizing bacteria are decreased with photodynamic treatment to plan a clinical trial in patients getting a hip joint arthroplasty and previous antisepsis.
Study Duration:	1 year
Study Schedule:	
 
• Project start (FPFV): July 2019 
 
◦ First participant: July 2019
 
◦ Last participant: June 2020
 
 
 
• Project end (LPLV): July 2020
 

Investigator(s):	
[name] Division of Infectious Diseases and Hospital Hygiene University Hospital Zurich [name] Email: [contact] [contact]
 
Dr. med [name] Department of Dermatology University Hospital of Zurich, Zurich University Hospital Zurich [name] Email: [contact] [contact]

Study Centre(s):	Single-center
Statistical Considerations:	Categorical data will be tested for differences using Fisher's exact or chi-squared tests, as appropriate, whereas continuous variables will be tested using Wilcoxon rank sum tests.
GCP Statement:	This study will be conducted in compliance with the protocol, the current version of the Declaration of Helsinki, the ICH-GCP as well as all national legal and regulatory requirements.

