## 2.4 Justification of Study Intervention

Skin swabs and small skin biopsies have only minimal risks and the PDT enjoys great popularity as it is well tolerated. Therefore, we select this promising treatment to investigate an innovative strategy to improve skin antisepsis in a pilotstudy. If we see that we have sterile cultures after PDT and skin antisepsis we will plan a larger prospective study based on these data.

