# 10 STATISTICAL METHODS

Categorical data will be tested for differences using Fisher's exact or chi-squared tests, as appropriate, whereas continuous variables will be tested using Wilcoxon rank sum tests.

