## 10.3 Planned Analyses

- As a pilot study, we plan to do descriptive statistics only.
- Categorical date will be tested for differences using Fisher's exact or chi-squared tests.
- Continuous variables will be tested using Wilcoxon rank sum tests.
- Data will be analyzed using Stata® version 14.2 (Stata Corporation, College Station, TX). Two-tailed P-values <0.05 are considered statistically significant.

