### 10.3.1 Datasets to be Analyzed, Analysis Populations

All Study participants that terminated the study (n = max 20 volunteers)

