### 10.3.2 Primary Analysis

Descriptive comparisons of microbiological data before and after PDT by [name], [name], and [name].

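### The primary before-after comparison is within-person, but the plan names only independent-sample tests, gives no paired estimate, and sets P<0.05 beside a promise of description only

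*Combined protocol and SAP*

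**What the plan says.** Section 10.3.2 defines the primary analysis as "Descriptive comparisons of microbiological data before and after PDT". The data are repeat groin scrapings from the same volunteers: at baseline, after PDT and antisepsis on day 0, and on days 7 and 21 (sections 3.2 and 5.2). The biopsy substudy takes tissue from the treated right groin and the untreated left groin of the same person (section 5.2).

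Tests are named in three places: the synopsis, section 10 and section 10.3. Each gives Fisher's exact or chi-squared for categorical data. For the rest, section 10 says "continuous variables will be tested using Wilcoxon rank sum tests" and section 10.3 repeats it: "Continuous variables will be tested using Wilcoxon rank sum tests". No section links a test to a comparison, and no paired test, within-person change or confidence interval appears.

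On inferential status, the synopsis says "There will be only descriptive statistics to see if numbers of colonizing bacteria are decreased with photodynamic treatment" and section 10.3 opens with "As a pilot study, we plan to do descriptive statistics only". The same list in section 10.3 then states "Two-tailed P-values <0.05 are considered statistically significant".

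The analysis set is "All Study participants that terminated the study (n = max 20 volunteers"). One stated condition for a larger study is "If we see that we have sterile cultures after PDT and skin antisepsis" (section 2.4). Sections 2.1 and 5.1 speak only of promising results.

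**The concern.** Two scrapings from one groin are not independent observations. Fisher's exact, chi-squared and rank sum treat them as if they came from different people. They use the before total and the after total, and discard the information on which volunteers changed and in which direction.

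A significance threshold beside a descriptive-only statement makes it likely that P-values will be printed, and the tests to hand do not fit the one comparison that section 10.3.2 names. More important for a pilot, before and after totals alone do not give the precision of the within-person change, which the planned hip arthroplasty trial would draw on.

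**Working it through.** **Inputs.** The plan gives a target of 20 volunteers (section 10.2) with no rate, effect size, standard deviation, correlation or power, so there is no stated calculation to reproduce. Section 7.1.1 gives PDT to 20. If the 10 controls of section 5.2 come out of the maximum of 20, only 10 receive it. A footnote to Figure 1 mentions 8 out of 10, with its referent not visible, so I use 8 as a low case. All rates, shifts, cut-points and correlations below are assumptions.

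**1. Same totals, different pairs.** Suppose growth in 16 of 20 before and 10 of 20 after.
- Fisher: P = 0.096.
- Uncorrected chi-squared: 40 × (16×10 − 4×10)² / (20×20×26×14) = 3.96, P = 0.047. The smallest expected count is 14×20/40 = 7, so this test qualifies under the usual rule of 5.
- Exact McNemar is 2 × P(X ≤ number up), with X binomial(down + up, ½). Mid-P subtracts the probability of the observed count.

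| Pairs | Exact McNemar | Mid-P | Paired 95% CI for the drop (Tango) |
|---|---|---|---|
| 6 down, 0 up | 2/64 = 0.031 | 0.016 | 9 to 52 points |
| 10 down, 4 up | 2×1471/16384 = 0.180 | 0.118 | −7 to 59 points |

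The unpaired (Newcombe) interval is 0.5 to 53 points in both rows. The named tests cannot tell the rows apart, and they fall on opposite sides of 0.05 themselves.

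**2. The reverse case.** Growth from 16 to 9 of 20, with 11 down and 4 up: Fisher 0.048 and chi-squared 0.022, against exact McNemar 2×1941/32768 = 0.118 and mid-P 0.077.

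**3. Power for growth yes/no,** 80% falling to 40%, correlation 0.5, by exact enumeration of the paired table:

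| Pairs | Fisher | Exact McNemar | Mid-P McNemar |
|---|---|---|---|
| 20 | 67% | 76% | 85% |
| 10 | 22% | 18% | 36% |
| 8 | 20% | 6% | 19% |

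At 20 pairs uncorrected chi-squared has 79%. Mid-P therefore gains about 85 − 79 = 6 points over it, and exact McNemar gains nothing. Most of the gap between Fisher and mid-P is Fisher's own conservatism.

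**4. Power for graded or continuous measures** (simulation, correlation 0.5, error about 1–2 points), rank sum v signed-rank:
- Normal data, 0.7 SD shift: 56 v 82% (20 pairs), 23 v 49% (10), 19 v 34% (8). The type I error of rank sum is about 1% instead of 5%.
- Four-level grade (none, +, ++, +++), 0.8 SD latent shift: 65 v 80% (20 pairs), 29 v 33% (10), 22 v 18% (8).

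**5. Five biopsy pairs.** The smallest two-sided P for rank sum is 2/C(10,5) = 2/252 = 0.008. For signed-rank it is 2/2⁵ = 0.0625. The named test can call a gland result significant where the paired rank test never could.

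**6. The sterile-culture condition.** If 0 of n grow, the exact upper 95% limit is 1 − 0.025^(1/n): 17% for 20, 31% for 10, 37% for 8.

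**7. Which scrapings are compared.** Section 3.2, item 1.1, fixes the immediate contrast as baseline against the state after both PDT and antisepsis; item 2.1 sets days 7 and 21 against baseline. Two things stay open. Section 4.1 speaks of the time immediately after PDT, and section 8.3.2 lists a scraping at that point as well as one after antisepsis. Sections 8.3.3 and 8.3.4 list a scraping before and another after that visit's antisepsis; their opening sentences name only the second, which does not match an unprepared baseline.

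**The case against.** The strongest reply is that the primary analysis specifies no test at all. It is called descriptive, the tests sit in general sections, and the design has contrasts for which they are valid: the 10 participants without PDT, if they are separate people (section 5.2, including the Figure 1 caption), and the outside reference study (sections 2.5 and 6). This stands in part. A reader might infer that the plan commits to unpaired tests on paired data; the documents do not say so, and the harm depends on P-values being given for before v after. But no section assigns the tests to the between-group contrast, section 7.1.2 says there is no control intervention, and a descriptive analysis of paired data still needs a paired summary.

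Three other strong readings also fail. One might infer that before and after are undefined, but section 3.2 defines the immediate contrast. One might infer inflated false positives, but with positive within-person correlation the named tests are conservative on average, although a single result can differ either way. One might infer a clear power loss for every outcome, but for growth yes/no the gain at 20 pairs is small once the plan's own chi-squared option is counted.

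**Conclusion.** The point holds and should be fixed. The named tests do not fit the comparison that the plan calls primary, no paired estimate is specified, and the descriptive-only statement conflicts with the significance rule.

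The size varies by outcome. For a roughly continuous measure at 20 pairs the loss is large: about 26 points of power under the assumed shift and correlation. For a coarse grade it is about 15 points at 20 pairs and small or reversed at 8–10. For growth it is about 6 points at 20 pairs with mid-P and nil with exact McNemar. At 8–10 pairs there is no gain for growth, apart from mid-P at 10.

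One might also infer that an invalid P-value would decide whether the next trial goes ahead. The stated conditions are promising results and sterile cultures, neither of which is a P-value. The main loss is therefore the within-person estimate and its precision. The textual gap is certain; the magnitudes are illustrative.

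**What to change.** In the synopsis and sections 10 and 10.3:

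1. For each within-person contrast, report the paired difference with a 95% CI and the numbers lower, unchanged and higher. If a P-value is given, use McNemar (exact or mid-P, chosen in advance) for growth or species presence, and Wilcoxon signed-rank for species count and grade.
2. State which scraping at days 7 and 21 is compared with which day 0 scraping: before-antisepsis with baseline, after-antisepsis with after-antisepsis. Settle whether the immediate time point in section 4.1 is before or after antisepsis.
3. Keep Fisher, chi-squared and rank sum for PDT v no-PDT participants (if separate people) and for the outside reference study.
4. Show the five biopsy pairs as individual paired differences.
5. Make estimates and intervals the main result, label every P-value exploratory, and report the number sterile after PDT plus antisepsis with an exact 95% CI.

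The cost is a few sentences, with no extra data or visits. The sponsor gives up any significance claim for the gland outcome and should expect little power gain for growth or grade if only 8–10 people receive PDT.

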### 10.3.1 Datasets to be Analyzed, Analysis Populations

All Study participants that terminated the study (n = max 20 volunteers)

### 10.3.2 Primary Analysis

Descriptive comparisons of microbiological data before and after PDT by [name], [name], and [name].

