Outcome(s):	
Primary outcome
 
 
1. Immediate effect of photodynamic treatment in combination with surgical antisepsis on bacterial skin colonization           
 
1.1. To quantitatively evaluate bacterial density and species before photodynamic treatment and after photodynamic treatment and antisepsis skin preparation
 
 
 
2. Long-term effect on bacterial skin colonization in the groin after photodynamic treatment           
 
2.1. To quantitatively evaluate bacterial density and species before and after photodynamic treatment (7 and 21 days)
 
2.2. To evaluate changes of sebaceous and sweat glands after photodynamic treatment on skin biopsies
 
 
 
 
Secondary outcome
 
 
3. To evaluate phylogenetic similarity of the microbiota on the dermis before and three weeks following photodynamic treatment
 

Study design:	Pilotstudy, open label, single center
Inclusion / Exclusion criteria:	
Inclusion criteria
 
Healthy male and female participants <math>\geq 18</math> years who
 
 
• volunteer for the pilot study in which a routine photodynamic treatment in the Department of Dermatology will be applied and effect of skin colonization will be analyzed, and
 
• an informed consent is signed by the participant (after information about the project).
 
 
Exclusion criteria
 
 
• Pregnant and lacting women
 
• Participants with inability to follow the procedures of the study, e.g. due to language problems, psychological disorders, dementia, etc.,
 
• Participants taking antibiotics in the 14 days prior to the photodynamic treatment or until follow-up at 21 days
 
• Participants who received oral retinoid therapy within the last 6 months
 
• Participants who received anti-inflammatory agents as NSAR within the 14 days prior and after the PDT
 
• Participants taking any photosensitizing drugs within 4 weeks prior to the photodynamic treatment (PDT)
 
• Participants who had a history of photosensitivity disorder
 
• Fitzpatrick's skin phototype V-VI
 

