### 5.2 Study Duration and Study Schedule

The expected duration of participant's participation is 35 days from first study visit to the last follow-up time to report side effects of photodynamic treatment. The screening visit can be any time before but at least 1 week before the first study visit. The study schedule is indicated below.

**Figure 1.** Flow chart

**Fig.1.** Study design of the PDT versus the control group

\* Only performed in 8 out of 10; \*\* only performed in 4 participants

At the day of inclusion, the voluntary participant will be informed and asked for signing the informed consent by [name] when fulfilling in- and exclusion criteria. This visit and the last visit (day 35 of the study) will be at the outpatient clinic for Infectious Diseases at the University Hospital Zurich. Demographic data (age, sex, current medications, and underlying diseases) will be noted.

Appointments for the photodynamic treatment (day 0) and the control visits (day 7 and 21) at the Department of Dermatology with Dr. [name] or at the Infectious Diseases department will be made

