#### **Study schedule:**

On day 0 with [name] and [name], a skin scraping of the groin will be performed and sent for microbiological culture. Then, 5% topical methyl aminolevulinate (MAL) as the photosensitizer will be applied for 3 hours under occlusion in the right groin of the patient. After the incubation, the photodynamic process will be started by irradiation of the area with 40J/cm^2 red light from a 633nm emitting LED during 13 minutes.

Immediately after the MAL-PDT, skin antisepsis will be performed. Antisepsis of the skin is performed with a povidone-iodine/alcohol solution (Betaseptic®, Mundipharma, Limburg, Germany) and repeated three times for a total duration of 3 minutes to imitate standard surgical antisepsis before a hip arthroplasty surgery. Skin scraping will be repeated after the 3rd antisepsis and 7 and 21 days later (study visit day 7 and 21) for bacterial cultures.

As a control group, we will take skin swabs before and after skin antisepsis without PDT in 10 participants.

On day 35 ( $\pm 7$  days) of the study, volunteers will be seen for the last study visit to document any adverse effects and to inform about the individual study result.

Substudy in 5 volunteers:

In the course of the study a total of three small skin biopsies are taken (3mm diameter each) from 5 volunteers. The time and locations of the performed biopsies will be

1. from the right groin immediately after the MAL-PDT or at day 7
2. from untreated control area in the left groin after the MAL-PDT (day 0 or 7)
3. from the MAL-PDT area on day 21 as the control after treatment.

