## 7.2 Administration of Study Intervention

### 7.2.1 Study Intervention

Details of study Intervention	Justification
1. Inguinal skin scraping before photodynamic treatment	Baseline microbiome data
2. Natural bacterial porphyrin fluorescence photography	Baseline fluorescence photography
3. Photosensitizer application, followed by fluorescence photography Photodynamic therapy (PHT) (1x) over 15 minutes at the dermatology ward	Treatment to kill bacteria and to reduce glands in order to reduce colonization bacteria
4. Skin antisepsis in the groin, skin scraping after antisepsis	To measure bacterial colonization to know the immediate effect of PDT
5. Punch biopsy  specimen of the MAL-PDT area (immediately after PDT) and of an untreated area as a control	To analyze size and structure of glands in the skin
6. Inguinal skin scraping and punch biopsy of the MAL-PDT area after 7 and 21 days	To measure bacterial colonization to know the long-term effect of PDT

 only in 5 participants

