## 10.1 Hypothesis

We hypothesize that photodynamic treatment improves skin antisepsis by reduction of persistent skin colonizing bacteria through the destruction of the sebaceous and sweat glands and by its bactericidal effects.

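### Section 10 puts the planned 10-participant control without PDT into no comparison, and a before/after change measured after PDT plus antisepsis cannot show what PDT adds to antisepsis

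*Combined protocol and SAP*

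**What the plan says.** **Immediate outcome.** The Synopsis defines outcome 1.1 as "To quantitatively evaluate bacterial density and species before photodynamic treatment and after photodynamic treatment and antisepsis skin preparation", and section 3.2 has the same definition. The heading of Outcome 1 in section 4.1 also refers to the combination with surgical antisepsis, although the swab line beneath it speaks of samples before and immediately after PDT.

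**How the result is to be read.** The table in section 7.2.1 justifies the scrape after antisepsis as "To measure bacterial colonization to know the immediate effect of PDT". Section 10.1 hypothesises that "photodynamic treatment improves skin antisepsis by reduction of persistent skin colonizing bacteria".

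**Control.** The study schedule in section 5.2 states: "As a control group, we will take skin swabs before and after skin antisepsis without PDT in 10 participants". The Figure 1 caption reads "Study design of the PDT versus the control group". The Synopsis, under Reference Intervention, adds the group to an external study in garbled wording: "In addition, we will take skin swabs before and after skin antisepsis without antisepsis in 10 participants". Sections 2.5 and 6 name that external study, which has no PDT, as the reference. Section 7.1.2 says there is no control intervention.

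**Analysis.** Section 10.3.2 gives only "Descriptive comparisons of microbiological data before and after PDT". Section 10.3.1 defines one analysis set of at most 20 and names no groups. Sections 10 and 10.3 list Fisher's exact, chi-squared and Wilcoxon rank sum tests without saying what is compared with what. No part of section 10 mentions the control group or the external study.

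**The concern.** The plan collects the data needed to ask whether PDT improves antisepsis, then specifies an analysis that does not use them. A before/after change on the post-antisepsis scrape describes PDT and antisepsis together. The hypothesis in section 10.1 and the justification in section 7.2.1 attribute the result to PDT.

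The pilot is meant to decide whether a trial in hip arthroplasty patients is worthwhile. Section 2.4 ties that decision to sterile cultures after PDT and antisepsis, a result to which antisepsis also contributes. Read alone, it does not say how much is due to PDT.

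**Working it through.** No figure in the plan can be reproduced here. Section 10.2 gives 20 volunteers with no rate, effect size or power. The check sets the sections side by side and adds simple arithmetic.

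**1. What each available contrast describes**

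| Contrast | What it describes | Assigned in section 10? |
|---|---|---|
| Before PDT v after PDT and antisepsis | The combined procedure | Yes, if 10.3.2 is read with the Synopsis and 3.2 |
| Before PDT v after PDT but before antisepsis | PDT alone, within person | Only if 10.3.2 means this scrape; not stated |
| After antisepsis, with PDT v without PDT | What PDT adds to antisepsis | No |

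Only the third row addresses section 10.1.

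**2. Size of the antisepsis component**

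Let *b* be the proportion of scrapes with growth at baseline and *a* the share of these that antisepsis alone turns negative. Assume that PDT is inert and that no baseline-negative scrape becomes positive.

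- Before/after drop in PDT participants: *b* - *b*(1 - *a*) = *ba*.
- Difference in post-antisepsis growth, PDT v antisepsis only, with the same *b* in both: *b*(1 - *a*) - *b*(1 - *a*) = 0.

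The documents give neither *a* nor *b* for groin scrapes. Taking *b* = 100% for illustration:

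| Positive after antisepsis alone | Before/after drop, inert PDT | PDT v antisepsis only |
|---|---|---|
| 90% | 10 points | 0 |
| 70% | 30 points | 0 |
| 50% | 50 points | 0 |
| 30% | 70 points | 0 |

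Conversely, suppose 30% are positive after PDT and antisepsis. The before/after drop is 100 - 30 = 70 points whatever PDT contributes. The PDT share of it is 30 - 30 = 0 points if antisepsis alone leaves 30% positive, and 70 - 30 = 40 points if it leaves 70%. The planned contrast cannot tell these apart.

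**3. Which day-0 scrapes are taken**

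The visit list in section 8.3.2 has a scrape between PDT and antisepsis. The skin antisepsis text in section 8.1 partly supports it, since it asks for scraping before and after the third antisepsis. The schedule in section 5.2, the table in section 7.2.1 and the study plan table in section 8.1 do not list it.

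**4. Who the 10 are**

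- *In addition to 20 PDT participants:* 20 + 10 = 30 people, against the maximum of 20 in sections 2.1 and 10.3.1.
- *Within the 20:* 10 + 10, which the Figure 1 note "Only performed in 8 out of 10" may suggest, but section 7.1.1 gives PDT to 20.
- *The same people as PDT participants:* fits sections 2.1, 2.7, 7.1.1 and 10.3.1, but sits badly with a figure that sets PDT against a control group.

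Figure 1 itself is not in the available text and may settle this. The first two readings give independent data, the third paired data.

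**5. Precision of the missing comparison (hypothetical counts, different people)**

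Take 7/10 positive after antisepsis only and 3/10 after PDT and antisepsis. The difference is 0.70 - 0.30 = 0.40. Wilson 95% limits are 0.397 to 0.892 and 0.108 to 0.603. The Newcombe limits are:

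- lower: 0.40 - √[(0.700 - 0.397)² + (0.603 - 0.300)²] = 0.40 - 0.429 = -0.029
- upper: 0.40 + √[(0.892 - 0.700)² + (0.300 - 0.108)²] = 0.40 + 0.272 = 0.672

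That is 40 points, 95% CI -3 to +67.

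**The case against.** The strongest reply has four parts.

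- *The outcome is deliberately the combination, in a descriptive pilot.* Where Outcome 1 means the combination, a before/after description matches it, and that stands. It does not cover sections 7.2.1 and 10.1, which attribute the effect to PDT.
- *A scrape between PDT and antisepsis may exist.* This stands in part. Section 10.3.2 says only before and after PDT, and sections 4.1 and 8.3.2 allow that scrape. If taken, it describes PDT alone within person. It does not show what PDT adds, because the bacteria that PDT removes might have been removed by antisepsis anyway. A reader might infer that the study's data cannot separate PDT from antisepsis in any way; the documents do not support that.
- *An antisepsis-only comparator is planned in the external study.* Sections 2.5 and 6 do say so, but section 10 does not say how it is used. Section 5.3 concedes that healthy volunteers' microbiome may differ slightly from that of hip arthroplasty patients.
- *The named tests fit a comparison of groups, and the analysis set does not exclude controls.* Both are true, but neither specifies a comparison.

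A reader might also take the 10 to be a separate group studied concurrently. Section 5.2 gives neither timing nor allocation and leaves open whether they are different people.

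**Conclusion.** The point holds for the immediate outcome. Section 10 names no comparator. On the post-antisepsis scrape, the before/after change equals the antisepsis effect when PDT is inert. That result is structural; only its size (10 to 70 points above) rests on assumed rates, full baseline growth and no new growth in baseline-negative scrapes. The analysis as written therefore does not answer section 10.1.

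Two stronger inferences are not supported. One is that the plan carries a calculable false-positive rate for PDT: sections 10.3 and 10.3.2 call the analysis descriptive, and any such rate would rest on assumed growth and clearance figures. The other is that antisepsis alone yields sterile cultures in 3 of 10 people, taken from the study cited in section 2.1 in which 7 of 10 volunteers had viable *C. acnes*. That figure concerns one species in dermal tissue, and absence of that species is not sterility. The Synopsis also reports that common antisepsis does not eliminate skin bacteria in the sponsor's ongoing study.

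This should be fixed before analysis. Confidence is high that the comparison is missing and lower on the group structure.

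**What to change.** 1. **Reconcile first.** Align the Synopsis (Reference Intervention) and sections 2.1, 2.7, 5.2, 7.1.1, 7.1.2, 8.1 (skin antisepsis), 8.3.2 and 10.3.1 on three things: whether there is a control group; whether its 10 participants are separate from, within, or the same people as the 20; and which day-0 scrapes are taken.
2. **Name the comparison in 10.3.2.** Estimate what PDT adds as the difference in post-antisepsis growth (yes/no and grade) with PDT versus antisepsis only, showing both baselines. For growth yes/no, give a 95% CI: Newcombe's interval for independent groups if they are different people, a paired interval if they are the same people. Label the result exploratory, imprecise and, as no random allocation is described, non-randomised.
3. **Give the other data defined roles.** Keep before/after as a description of the combined procedure, report any scrape between PDT and antisepsis as PDT alone, and state how the external study serves as reference.
4. **Read the sterile-culture criterion in section 2.4 beside the antisepsis-only result.**

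**Cost.** No samples beyond those section 5.2 already plans. Section 1.15 makes changes to endpoints or to the form of statistical analysis subject to ethics committee approval, so an amendment is needed. The interval will be wide and the comparison remains open to group differences, so it should be read as an estimate and not as a test.
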